6.7.5 Chest Wall Pain and/or Rib Fracture

Chest wall pain presents either as a result of intercostal neuropathy, inflammation, or rib fracture (focal radiation induced osteoporosis can result in both occult and obvious rib fractures generally propagated by severe coughing/sneezing episodes or chest wall trauma). The pain typically occurs several months after treatment and may last several more months. The chest pain will be scored per CTCAE, v. 4.

6.7.6 Radiation-Induced Toxicity of Heart and Esophagus

Radiation-induced toxicity of heart and esophagus will be scored per CTCAE, v. 4.

6.8 Radiation Therapy Adverse Event Reporting

All AE reporting on the study case report forms (CRFs) should follow grading criteria instructions on the specific CRF. Note: All adverse events will be scored according to CTCAE, v. 4, which can be accessed on the RTOG web site: <http://www.rtog.org/ResearchAssociates/AdverseEventReporting.aspx> (scroll to the bottom of the page).

6.8.1 Adverse Events (AEs)

Definition of an AE: Any unfavorable and unintended sign (including an abnormal laboratory finding), symptom, or disease temporally associated with the use of a medical treatment or procedure regardless of whether it is considered related to the medical treatment or procedure (attribution of unrelated, unlikely, possible, probable, or definite).

AEs, as defined above, experienced by patients accrued to this protocol should be reported on the AE section of the appropriate case report form (see Section 12.1).

NOTE: If the event is a Serious Adverse Event (SAE) [see next section], further reporting will be required. Reporting AEs only fulfills Data Management reporting requirements.

6.8.2 Serious Adverse Events (SAEs)

Definition of an SAE: Any serious adverse experience occurring during any part of protocol treatment and 30 days after whether or not related to the study drug that results in any of the following outcomes:

- Death;
- A life-threatening adverse drug experience;
- Inpatient hospitalization or prolongation of existing hospitalization;
- A persistent or significant disability/incapacity;
- A congenital anomaly/birth defect.

Important medical events that may not result in death, be life threatening, or require hospitalization may be considered an SAE, when, based upon medical judgment, they may jeopardize the patient and may require medical or surgical intervention to prevent one of the outcomes listed in the definition.

SAE reporting is safety related and separate and in addition to the Data Management reporting requirements as outlined in the previous AE reporting section.

6.9 Serious Adverse Event (SAE) Reporting Requirements

It is the responsibility of the investigator to document all adverse events which occur during the study.

In addition to standard practice of recording AEs and SAEs on the case report form, this study will utilize an RTOG SAE Report Form for reporting of SAEs. The SAE Report Form, SAE Reporting Guidelines, and SAE Report Form Instructions are available on the RTOG web site, www.RTOG.org.

6.9.1 Reporting SAEs

Any SAE that occurs during any part of protocol treatment and 30 days after whether or not related to the study treatment must be reported by the investigator. In addition, any SAEs which occur as a result of protocol specific diagnostic procedures or interventions also must be reported.

The SAE report should comprise a full written summary, detailing relevant aspects of the SAEs in question. The SAE summary also must include the investigator's assessment of expectedness and relatedness to specific protocol treatment (e.g. radiation or surgery). When applicable, information from relevant hospital case records and autopsy reports should be included. Initial and follow-up information, when it becomes available, should be faxed to the RTOG SAE Fax Line [contact] or e-mailed to [contact]. Each participating site must report the SAE to their regulatory authority. RTOG will report the SAE to the FDA.

SAEs brought to the attention of the investigator at any time after cessation of treatment and considered by the investigator to be related or possibly related to treatment also must be reported.

All SAEs must be reported to RTOG by facsimile to the RTOG SAE Fax Line [contact] or e-mailed to [contact] within 24 hours. RTOG will complete a preliminary review of the SAE details and may contact the site with suggested revisions.

6.9.2

Assessment of Causality and Expectedness

Every effort should be made by the investigator to explain each SAE and assess its expectedness and relationship, if any, to study treatment. Causality should be assessed using the following categories: no (not related), or yes (reasonable possibility).

The investigator may change his/her opinion of expectedness and/or causality in light of follow-up information, by amending the SAE Report Form.

7.0 DRUG THERAPY

Not applicable to this study.

8.0 SURGERY (10/22/14)

8.1 Surgical Resection Guidelines

8.1.1 Resection Procedures

Anatomic resection, i.e. lobectomy, bilobectomy, or pneumonectomy, will be performed at the discretion of the responsible thoracic surgeon. The final goal of surgery is complete resection, i.e., removal of the primary tumor with at least a 2 cm margin together with mediastinal and hilar nodal dissection or systematic mediastinal and hilar nodal sampling.

A radical resection is defined as a **complete resection** if all of the following apply:

- Free resection margins proven microscopically: resection margins should be considered to be the bronchial, venous and arterial stumps, peribronchial soft tissue, any peripheral margin near the tumor or any additionally resected tissue;
- There should be no extracapsular extension of tumor in lymph nodes removed separately or those at the margin of the main lung specimen;
- The highest mediastinal lymph node that has been removed must be negative.

The resection is considered an **incomplete resection** if any of the following apply:

- Tumor involvement of resection margins;
- Extracapsular extension of tumor in lymph nodes removed separately, or those at the margin of the main lung specimen;
- Lymph nodes known to be positive but not removed (this would be an R2 resection if recognized by the surgeon);
- Positive cytology of pleural or pericardial effusions.

The lung resection is considered an **uncertain resection** if the resection margins are proved to be free of disease microscopically, but one of the following applies:

- The intraoperative lymph node evaluation has been less rigorous than systematic nodal dissection or lobe-specific systematic nodal dissection as described below;
- The highest mediastinal lymph node removed is positive;
- The bronchial margin shows carcinoma in situ;
- Pleural lavage cytology is positive.

8.1.2

Intra-Operative Nodal Staging

According to the guidelines of the American and European Societies of Thoracic Surgeons, a systematic nodal dissection is recommended in all cases [167]. All the nodal stations are excised and put in different vials with separate labeling. The highest removed mediastinal node should be identified. After pathological examination of the lymphatic tissue specimens, the number of involved lymph nodes and nodal stations, and the status of the nodal capsule should be documented.

Systematic nodal sampling with a lobe-specific systematic nodal approach will only be acceptable for a peripheral squamous T1 tumor. A lobe-specific systematic nodal dissection implies dissection and histological examination of intrapulmonary (lobar-level 11, interlobar-level 12 and segmental-level 13-14) and hilar nodes (level-10) and, at least, three of the following mediastinal nodal stations depending on the lobar location of the primary tumor.

- The right upper and middle lobes: the subcarinal (level-7) and right superior/inferior pretracheal nodes (level-2 and -4)
- The right lower lobe: the subcarinal (level-7) and right inferior pretracheal nodes (level- - 4) and either the paraesophageal (level-8) or pulmonary ligament (level-9) nodes.
- The left upper lobe: subcarinal (level-7), subaortic (level-5)/paraaortic (level-6), left inferior pretrachial (level-4) and anterior mediastinal nodes (level-3a).
- The left lower lobe, subcarinal, left inferior pretrachial (level-4), paraesophageal (level-8) and pulmonary ligament nodes (level-9).

8.1.3

Mediastinal Nodal Sampling

Mediastinal nodal sampling is allowed.[168]. When sampling is elected, hilar and 3 high risk nodal regions should be sampled based on the location of the primary tumor:

- The right upper and middle lobes: the subcarinal (level-7) and right superior/inferior pretracheal Nodes (level-2 and -4);
- The right lower lobe: the subcarinal (level-7) and right inferior pretracheal nodes (level- - 4) and either the paraesophageal (level-8) or pulmonary ligament (level-9) nodes;
- The left upper lobe: subcarinal (level-7),subaortic (level-5)/paraaortic (level-6), left inferior pretrachial (level-4) and anterior mediastinal nodes (level-3a);
- The left lower lobe, subcarinal, left inferior pretrachial (level-4), paraesophageal (level-8) and pulmonary ligament nodes (level-9).

Both nodal dissection and sampling specimens should include, at least, 6 nodes, 3 removed from intrapulmonary and/or hilar stations and 3 removed from mediastinal stations, one of which must be the subcarinal station. Numbering and /or nomenclature outlined in the regional nodal stations / lymph node map definitions should follow nodal zones defined by IASLC/AJCC [169; 270] in Appendix VI.

8.1.4

Pathology Assessment Guidelines

The surgeon needs to report the time of excision out of the body on the Surgery/Pathology Study Form.

Primary tumor tissue and normal lung tissue will be submitted to trial Tissue Bank within 14 days after surgery for those patients who have consented to banking their tissues (Appendix I) .

The removed lymph nodes undergo histopathological evaluation as follows [167]:

1. As a first step, all resected intrapulmonary, hilar, and mediastinal nodes should be examined macroscopically. In the presence of gross tumor, one hematoxylin-eosin (HE) stained section should be performed at the most macroscopically suspicious site to demonstrate the metastasis and its possible extracapsular extension.

2. If the macroscopic evaluation does not show any suspicion of metastasis, a single section of a node should be avoided. The probability to detect a metastasis on center section is related to the size of the lymph node, the size of the lesion, and the location of the tumor within the node. To avoid this problem, it is recommended to perform several sections of the nodes, 2-mm slices in the longitudinal plane and to examine each block separately. Thin sections of 2 mm may increase the workload of the pathologist but increase the detection rate of metastases. Small nodes can be sliced and embedded in one block if possible.
3. There are different methods to detect additional metastatic deposits in lymph nodes like serial sectioning or immunohistochemistry (IHC). IHC using a cocktail of cytokeratins such as the anti-epithelial antibody mAb Ber-Ep4, AE1/AE3 is a sensitive and specific method for detecting isolated tumor cells or clusters of cells. Three levels of section are enough for this analysis.

8.1.5 Treatment for Unexpected N1 and N2 disease

If a patient has unexpected nodal positive disease, his/her further care should be discussed by a multidisciplinary team. Based on the results of phase III randomized trials and recent meta-analyses, cisplatin-based adjuvant chemotherapy improves survival in patients with stage II or III NSCLC [170-177] and such treatment should be offered if the patient is medically fit. Considering that the literature is evolving, the consideration of adjuvant chemotherapy should follow NCCN guidelines.

8.1.6 Post-Operative Care and Follow Up

The patient should undergo inpatient pulmonary rehabilitation [178] and receive prophylactic doses of low molecular weight heparin (LMWH) until discharge [179, 180]. The patient should be followed-up for complications related to surgery, and undergo surveillance at regular intervals with imaging and review of symptoms. Smoking cessation after curative intent therapy to prevent a second primary lung cancer is strongly supported by the available evidence [181].

8.3 Adverse Events Associated with RODS

Atelectasis, lung infection, pneumonitis, dyspnea, adult respiratory distress syndrome, pleural infection, thromboembolic event, myocardial infarction, ventricular arrhythmia, arterial injury, venous injury, wound infection, bronchopleural fistula, postoperative hemorrhage, sepsis, recurrent laryngeal nerve palsy, intraoperative respiratory injury, changes in pulmonary function tests (e.g. forced expiratory volume (FEV1) decreased; carbon monoxide diffusion capacity (DLCO) decreased; vital capacity abnormal).

8.4 Surgery Adverse Event Reporting Requirements

See Section 6.9 for details.

9.0 OTHER THERAPY

9.1 Permitted Supportive Therapy

All supportive therapy for optimal medical care will be given during the study period at the discretion of the attending physician(s) within the parameters of the protocol and documented on each site's source documents as concomitant medication.

9.1.1 Cytotoxic Therapy

Cytotoxic therapy is not recommended for patients with stage IA (T1N0) disease. Patients with unexpected pathologic stage II or III disease should be offered adjuvant cisplatin-based chemotherapy, although there will be no primary, chemotherapy-related endpoints for this trial. Adjuvant chemotherapy for patients with stage IB NSCLC is controversial [188-191] but is sometimes offered to patients with higher-risk T2 tumors (> 4 cm) in routine clinical practice. To be consistent for trial treatment, adjuvant therapy is not recommended for patients with

clinical stage T1N0 and pathologic stage T2N0 tumors. The adjuvant chemotherapy regimen and the timing of chemotherapy will be at the discretion of the treating oncologist. However, docetaxel and gemcitabine containing regimens should be avoided due to concerns of exacerbating radiation lung injury. Otherwise, any cisplatin/carboplatin-based 2-drug regimen is considered acceptable (e.g. cisplatin/etoposide, carboplatin/paclitaxel, cisplatin/paclitaxel, cisplatin/pemetrexed, carboplatin/pemetrexed, cisplatin/vinorelbine).

9.1.2

Salvage Therapy

If a patient has disease progression after trial treatment (either RODS or SBRT), salvage therapy should be implemented per standard of care. Salvage therapy could include multimodality care, such as surgical resection, radiation (including SBRT) and systemic therapy based on the stage of the disease, per NCCN guidelines.

9.2

Non-permitted Supportive Therapy

9.2.1

Molecularly Targeted Therapy

No molecularly targeted therapy is planned for the patients treated on this trial. The addition of molecularly targeted therapy is not permitted, except in the setting of another clinical trial or progression of disease. Patients may be entered on appropriate trials of adjuvant therapy with either cytotoxic or molecularly targeted therapy.

9.2.2

Other Cancer Therapy

Aside from the therapy outlined above for surgical resection, SBRT, and systemic therapy, patients must not receive other concomitant local or regional antineoplastic therapy (including standard fractionated radiotherapy, non-approved systemic therapy, and surgery except as described in this protocol) except at disease progression.

11.0 PATIENT ASSESSMENTS

11.1 Study Parameters: See Appendix II.

11.1.1 Details of Follow-Up Evaluations

11.1.1.1 In follow up, PET and CT scans are required to document disease relapse/progression. Biopsy of the relapse/progression site is encouraged, but not required. Submission of the biopsy report (if applicable) and scan reports is required (see Schedule of Forms). Submission of imaging studies (scans with recurrent disease and the scans used for reference) is required for patients with recurrent disease.

Chest CT with IV contrast will be performed at least at 3, 6, 9, 12, 18, 24, and 36 months after completion of treatment (the date of surgery or at the last day of SBRT) per current standard of care. Response evaluation after SBRT can sometimes be difficult as fibrosis and subclinical radiographic changes are observed in a majority of patients. A solid pattern of fibrosis often may be misinterpreted as recurrent disease [267]. Regular radiological follow-up is required to establish local control. 18F-FDG PET can be helpful in distinguishing fibrosis from tumor recurrence, but treated volumes can show 18F-FDG uptake related to therapy for at least 12 months after treatment [162]. Careful radiological follow-up of patients is paramount in patients treated by RODS, as salvage surgery or definitive chemoradiotherapy might still be possible in case of local or regional recurrence [268-269].

11.1.1.2 In follow up, pulmonary function tests should be done per the treating physician's discretion.

11.1.1.3 After treatment is completed, patients will be seen in follow up every 3 months for years 1-2 years, every 6 months for year 3, then annually until publication of study results.

11.2 Measurement of Response

11.2.1 Guidelines for Assessing Treatment Response after SBRT

11.2.1.1 CT Tumor Response

Tumor response on CT will be assessed per RECIST 1.1, as described below; see http://ctep.cancer.gov/protocolDevelopment/docs/recist_guideline.pdf for additional details.

- Complete Response (CR): Disappearance of all target lesions. Any pathologic lymph nodes (whether target or non-target) must have reduction in short axis to <10 mm)
- Partial Response (PR): At least a 30% decrease in the sum of diameters of target lesions, taking as reference the baseline sum diameters.
- Progressive Disease (PD): At least a 20% increase in the sum of diameters of target lesions, taking as reference the *smallest sum on study* (this includes the baseline sum if that is the smallest on study). In addition to the relative increase of 20%, the sum must also demonstrate an absolute increase of at least 5 mm. (*Note:* the appearance of one or more new lesions is also considered progression).
- Stable Disease (SD): Neither sufficient shrinkage to qualify for PR nor sufficient increase to qualify for PD, taking as reference the smallest sum diameters while on study.

11.2.1.2 PET Tumor Response

Guidelines for assessing post-SBRT changes on PET/CT will be per the table below, defined by Kong, et al. at the University of Michigan [257], using the blood pool in the aortic arch as a reference. This system is considered to be more reproducible than that of PERECIST [258] which uses the liver as a reference. The aortic arch is also less likely to be confounded by disease conditions in the liver which may increase FDG-activity. Metabolic tumor volumes will also be assessed and recorded.

PET Tumor Response of Irradiated Target Lesions

Complete Metabolic Response (CMR)	Tumor FDG-activity decreased to less than mean background of the aortic arch blood pool.
Partial Metabolic Response (PMR)	At least a 30% decrease in the maximum of relative tumor FDG-activity of target lesions
Progressive Metabolic Disease (PMD)	At least a 20% increase in the maximum of relative tumor FDG-activity of target lesions
Stable Metabolic Disease (SMD)	Neither sufficient reduction to qualify for MPR nor sufficient increase to qualify for MPD

The percentage of decrease or increase was globally estimated based on readings of (tumor activity-aorta activity)/aorta activity.

11.2.2 Local regional tumor control is defined as freedom from local-regional recurrence after RODS and freedom from progression of local primary tumor and disease occurrence at nodal regions after SBRT.

Local-regional recurrence after RODS includes recurrence, defined by CT, confirmed by PET/CT whenever possible, i.e., development of tumor masses at the site of resection, or hilum (N1 nodal region), mediastinum (N2-N3 nodes), or ipsilateral supraclavicular fossa for upper lobe tumors (N3 nodes), or within 3 cm of the staple line of RODS.

Local regional progression after SBRT includes tumor progression on CT per RECIST criteria, confirmed by PET/CT, within the same lobe, hilum (N1 nodes), mediastinum (N2-N3 nodes), or ipsilateral supraclavicular fossa for upper lobe tumors (N3 nodes), or within 3 cm of original PTV.

Local progression is defined as at least a 20% increase in the sum of diameters of the target lesions, taking as reference the smallest sum on study (this includes the baseline sum if that is the smallest on study). In addition to the relative increase of 20%, the sum must also demonstrate an absolute increase of at least 5 mm. (Note: the appearance of one or more new lesions is also considered progression).

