The vast majority of patients have radiographic changes during follow-up scan, such as experienced some degree of atelectasis (collapse) of lung downstream from the area of treatment. This was felt to be related to bronchial injury of bronchi or bronchioles within or near the treated tumor. By unknown mechanisms over a period of 3-6 months, pulmonary parenchyma distal to the site of bronchial injury results in this focal lung collapse. The majority of patients are asymptomatic. In others, the injury apparently correlated to a drop in diffusing capacity and arterial oxygen tension on pulmonary function tests. This process of collapse may not be reversible, is mostly likely associated with large fraction sizes, as reported from Indiana University. This is the justification of using smaller fraction sizes in this study.

Bronchial injury with subsequent focal collapse of lung may impair overall pulmonary status. The consequences of bronchial toxicity, e.g. cough, dyspnea, hypoxia, impairment of pulmonary function test parameters, pleural effusion or pleuritic pain (associated with collapse), will be graded and reported on adverse event forms based on CTCAE, 4.

Bronchial injury also makes further assessment of tumor response more difficult as the collapsed lung approximates the treated tumor. Because atelectatic lung and tumor have similar imaging characteristics, radiology reports will often describe the overall process as progressive disease while the actual tumor may be stable or shrinking. A PET scan can be very useful to minimize and avoid such mischaracterization. As indicated, endoscopic exam can be applied for further assessment.

6.7.3

Changes in Pulmonary Function Tests

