12.1 Summary of Data Submission (6-AUG-2018)

Item	Due
Initial Evaluation Form (I1) Pathology Report (P1)	Within 2 weeks of registration
Radiotherapy Form (T1)	Within 1 week of RT end
Surgical Form (S1) Surgical Procedure Report (S2) Surgical Pathology Report (S5) NOTE: The S2 and S5 should be de-identified and emailed to [contact] as PDF files	Within 4 weeks after protocol surgery
Follow-up Form (F1)	Every 3 months for years 1-2 years, every 6 months for year 3, then annually until publication of study results

12.2 Summary of Dosimetry Digital Data Submission (Submit to RTOG Headquarters; see Section 12.2.1) (6-AUG-2018)

Item	Due
Preliminary Dosimetry Information (DD) Digital Data Submission – Treatment Plan submitted in DICOM format to RTOG via TRIAD, exported from treatment planning machine by Physicist Digital data submission includes the following: 
• Planning CT• RT Structure File including all required tumor volumes and critical normal structures• RT Plan File for final plan• RT Composite Dose File for treated beams• Digital DVH data including all required tumor volume and critical normal structures• Digital Data Submission Form (DDSI) [on the RTOG website, Foundation study 3502, under Forms]	Within 1 week of start of RT

Final Dosimetry Information Radiotherapy Form (T1) Daily Treatment Record (T5) [Copy of daily treatment chart submitted via email to [contact].]	Within 1 week of end of RT
PET and/or CT progression scans (MR) PET and/or CT progression reports (ME) Digital Data Submission Form (DDSI) [on the RTOG web site, Foundation study 3502, under Forms]	At time of progression
NOTE: For all digital data submissions (preliminary, final Dosimetry or PET/CT scans for progression), sites must complete a Digital Data Submission Form (DDSI) via the RTOG web site. Also, sites will notify RTOG via e-mail [contact] after any digital data is submitted. The e-mail must include study number, site name, and case numbers.	
Modified digital patient data as required by RTOG will be submitted via TRIAD.	

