APPENDIX II: STUDY PARAMETER TABLE: *See section 11.1 for details and exceptions

Assessments	Within 6 wks prior to registration, unless otherwise noted	Arm 1				Arm 2				Both Arms
		Prior to surgery in clinic OR Pre-Op OR prior to surg.remove of tumor	Intra-Op after surgical removal of tumor	Prior to dis-charge	4-6 wks Post-Op	Prior to 1st fraction of SBRT	After 3 rd fraction of SBRT	After all SBRT (the last day)	4-6 weeks after end of SBRT	
History & Physical	X				X				X	X
Thoracic Surgeon evaluation	X									
Document weight	X				X				X	X
Performance Score	X				X				X	X
PFTs (with DLCO)	X									X*
FDG-PET/CT scan	Within 4 wks				X					At 3, 12, 24 mos.
CT of chest/upper abdomen, with contrast	Within 4 wks				X					Chest CT with contrast at 3,6,9, 12, 18, 24, 36 mos.
EBUS	Within 4 wks prior to treatment									
Adverse event assessment					X			X	X	X
Pregnancy test, if applicable	Within 72 hrs.									
†Blood for research		X	X	X	X	X	X	X	X	
†Tissue for banking	For Both Arms: prior to treatment									

†For patients who consent to participate in the specimen banking component of the study; see Appendix I.

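### The PET/CT confirmation rule for the primary endpoint differs by arm and between sections, and no rule covers a CT-positive event that PET does not confirm

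*Combined protocol and SAP*

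**What the plan says.** Section 13.1.1 sends the primary endpoint to section 11.2.2, which states a separate event rule for each arm.

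- **Surgery (RODS), 11.2.2:** "Local-regional recurrence after RODS includes recurrence, defined by CT, confirmed by PET/CT whenever possible".
- **SBRT, 11.2.2:** "Local regional progression after SBRT includes tumor progression on CT per RECIST criteria, confirmed by PET/CT, within the same lobe". No feasibility qualifier is attached.
- **Closing paragraph of 11.2.2:** defines local progression by size increase or new lesions and sets no PET condition.
- **Both arms, 11.1.1.1:** "In follow up, PET and CT scans are required to document disease relapse/progression". On biopsy it says: "Biopsy of the relapse/progression site is encouraged, but not required".
- **Submission list at progression, 12.2:** "PET and/or CT progression scans (MR) PET and/or CT progression reports (ME".
- **Schedule, Appendix II:** "Chest CT with contrast at 3,6,9, 12, 18, 24, 36 mos", with follow-up FDG-PET/CT at 3, 12 and 24 months.

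Section 11.2.3 gives a second classification of failures as local, regional nodal or distant. Section 13.5.2 uses it for the evaluation of failure patterns.

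**The concern.** This is a non-inferiority comparison of two event counts, so an event should count on the same evidence in each arm. Here the same finding, a CT-positive recurrence without a confirming PET, appears to count after surgery and is doubtful after SBRT. Few failures are expected, so one or two events handled differently can change the conclusion.

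The second difficulty is that 11.2.2 and 11.2.3 place some recurrences in different categories. A site using the failure table and an analyst using the endpoint definition could classify the same patient differently.

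**Working it through.** **1. The confirmation rules side by side**

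| Source | RODS | SBRT |
|---|---|---|
| 11.1.1.1 | PET and CT required | PET and CT required |
| 11.2.2, arm sentences | CT; PET/CT if feasible | CT per RECIST plus PET/CT |
| 11.2.2, closing paragraph | no PET condition | no PET condition |
| 12.2 (submission list) | PET, CT or both | PET, CT or both |

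None of these says what happens when PET is missing, negative or equivocal. The case is foreseeable: of the six chest CTs due by 24 months (3, 6, 9, 12, 18, 24), three (6, 9, 18) have no scheduled PET.

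**2. Direction**

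Relative to the surgical rule, an added PET condition can only remove SBRT events, which favors non-inferiority. Two features act the other way. Fibrosis, or therapy-related tracer uptake, may be read as recurrence after SBRT. Also, 11.2.2 counts tumor anywhere in the same lobe after SBRT, with no matching zone for surgery beyond 3 cm of the staple line. The documents do not fix the net sign.

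**3. The plan's own sample size**

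Section 13.3 gives control of 90% and 75%, a 15-point margin and 36 per arm. A one-sided 0.20 pooled two-proportion test of 0.90 against 0.75 with 80% power gives 35.6, rounded up to 36. A non-inferiority formula with 90% in both arms at one-sided 0.10 gives 36.06, close to 36. Section 13.3 does not clearly state the false non-inferiority level, so both levels are shown below.

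**4. Sensitivity to lost SBRT events (loss rates assumed)**

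Exact enumeration of two binomials, n = 36 per arm. Declare non-inferiority if (pS − pR + 0.15)/SE ≥ z(1−α), with SE = √[pS(1−pS)/36 + pR(1−pR)/36]. True control is 0.90 for RODS and 0.75 for SBRT, so expected failures are 36 × 0.10 = 3.6 and 36 × 0.25 = 9. If a share u of SBRT failures is not counted, apparent SBRT control is 1 − 0.25(1 − u).

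| SBRT events lost | Patients | False NI, α = 0.10 | False NI, α = 0.20 |
|---|---|---|---|
| 0% | 0 | 0.103 | 0.208 |
| 5% | 0.45 | 0.131 | 0.253 |
| 10% | 0.9 | 0.165 | 0.303 |
| 20% | 1.8 | 0.250 | 0.420 |

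An example of one event deciding the result: with 4 RODS failures, 5 SBRT failures give (31/36 − 32/36 + 0.15)/0.0779 = 1.57, and 6 give (30/36 − 32/36 + 0.15)/0.0813 = 1.16. The cut-off at α = 0.10 is 1.28. At α = 0.20 (cut-off 0.84) the change falls between 6 failures (1.16) and 7 (0.79). These cases were chosen at the boundary.

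**5. Sensitivity the other way**

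With true control 0.90 in both arms, power is 0.789 (α = 0.10) or 0.907 (α = 0.20). One extra SBRT event on average, from over-calling, lowers control by 1/36 and power to 0.629 or 0.799.

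**6. How often a CT-only visit would come first**

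Assume a constant hazard with 75% control at 24 months. The chance of failing in months 3–6, 6–9 or 12–18, divided by the chance of failing by 24 months, is 0.508, or 4.6 of 9 SBRT failures. This is the share first seen at a visit without scheduled PET. It is not a loss rate.

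**7. The 11.2.3 table against 11.2.2**

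| Recurrence | 11.2.2 | 11.2.3 |
|---|---|---|
| Another ipsilateral lobe, 2–3 cm from PTV | local-regional | distant |
| Reference for that row after RODS | staple line | PTV, which RODS patients lack |
| Supraclavicular | ipsilateral, upper-lobe tumors | either side, any lobe |
| Port site or wound | not listed | local failure |

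The footnotes to the table compare it with another trial and do not reconcile it with 11.2.2.

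**The case against.** **A stricter rule after SBRT may be deliberate.** Section 6.7.2 explains that collapsed lung can be reported as progression, and adds: "A PET scan can be very useful to minimize and avoid such mischaracterization". Section 11.1.1.1 makes the same point about fibrosis. This stands as a reason for PET after SBRT. It does not settle how an unconfirmed event counts, and 11.1.1.1 itself cautions that "treated volumes can show 18F-FDG uptake related to therapy for at least 12 months after treatment".

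**A common rule already exists.** A reader might infer that the plan has none. That goes too far: 11.1.1.1 requires PET and CT at relapse in both arms. What remains is that 11.2.2 departs from it for one arm.

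**CT-only SBRT events are not clearly excluded.** A reader might infer that they are. The closing paragraph of 11.2.2 has no PET condition, so the text is ambiguous. Likewise, 12.2 is a submission list and does not make a CT-only event a valid endpoint.

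**The practical loss may be small.** The endpoint is binary at 2 years, PET is required at relapse, and it is scheduled at 12 and 24 months. Most true relapses first seen on CT could still be confirmed in time. This stands, and it is why the 51% visit share must not be read as events lost.

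**The table does not govern the primary endpoint.** Section 13.1.1 cites 11.2.2, and 13.5.1 analyses time to local-regional failure under the primary endpoint heading. This also stands, and it limits the table conflict mainly to secondary endpoints.

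**Conclusion.** The confirmation rule for the primary endpoint is inconsistent across 11.1.1.1, 11.2.2 and 12.2, it is unequal by arm in 11.2.2, and it is silent on CT-positive events that PET does not confirm. It should be corrected.

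A reader might infer that the trial is biased toward SBRT. The documents do not support that: the confirmation wording alone points that way, but the opposing features leave the net direction unknown. The size is unknown too. The 5–20% losses are assumed values, and the results rest on 36 per arm, an unpooled Wald margin test, the plan's 90% and 75% rates, and one-sided levels of 0.10 and 0.20. If every relapse receives a confirming PET, the unequal wording has no effect. The calculations show only that a shift of about one event matters at this sample size.

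The conflict between 11.2.2 and 11.2.3 affects patterns of failure and time to distant metastases. It reaches the primary count only if sites code events by the table.

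**What to change.** 1. In 11.2.2, apply the existing 11.1.1.1 requirement to both arms by deleting the feasibility qualifier for RODS, and make the closing local-progression paragraph subject to the same rule.
2. Primary analysis: in both arms, count events confirmed by PET/CT, or by biopsy where one was done.
3. Sensitivity analysis: in both arms, count all CT-defined events, including those with missing, negative or equivocal PET.
4. Align the 12.2 wording with 11.1.1.1.
5. Reconcile 11.2.3 with 11.2.2: one distance for local-regional versus non-primary-lobe failure, a staple-line reference for RODS, one supraclavicular rule and one port-site rule. List which 11.2.3 categories count as local-regional.

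The cost is wording in three sections, one sensitivity analysis and some recoding. PET and CT at relapse, and submission of scans, scan reports and any biopsy report, are already required.

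A common rule removes the between-arm difference but not shared under-counting. If 10% or 20% of events were lost in both arms, false non-inferiority would still be 0.139 or 0.186 at α = 0.10, and 0.268 or 0.343 at α = 0.20. The sensitivity analysis would show whether this matters. CT-only events are kept out of the primary count because of the over-calling risk after SBRT shown in step 5 of the working.
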